## Study Design

CSSC-001 is a two-arm, parallel-group, multi-center, randomized superiority trial in which outpatient adults with recent exposure to SARS-CoV-2 but no current infection will be randomized to receive either human coronavirus immune plasma (HCIP) or control (SARS-CoV-2 non-immune) plasma. This randomized, double-blind, controlled, phase 2 trial will assess the efficacy and safety of HCIP to reduce the cumulative incidence of the development of COVID-19 during study follow-up. Adults 18 years of age or older, with high risk exposure (see below for definition) to person with COVID-19 within 96 hours of enrollment (and 120 hours of receipt of plasma). A total of approximately 500 eligible subjects will be randomized in a 1:1 ratio to either HCIP or control plasma.

**High risk exposure will be defined** as currently defined by CDC and modified as the CDC makes changes. Currently this includes any close contact exposure (as defined by CDC guidelines) to person with COVID-19. Health Care Personnel (HCP) are defined as physicians, nurses, nursing assistants, therapists, technicians, emergency medical service personnel, dental personnel, pharmacists, laboratory personnel, autopsy

personnel, students, trainees and contractual staff. Persons not directly involved in patient care such as clerical, dietary, housekeeping, laundry, security, maintenance, billing, and volunteers, but who are potentially exposed to SARS-CoV-2 in the healthcare setting, also fall under the category of HCP in this protocol.

*Primary Outcome:*

- The primary outcome of CSSC-001 will be the cumulative incidence by day 28 of the development of COVID-19 (symptoms compatible with infection and/or RT-PCR positive) regardless of disease severity comparing those randomized to HCIP to those who are transfused with control plasma.

*Secondary Outcome:*

- Compare the cumulative incidence of disease severity between those randomized to HCIP and control plasma. Severity of disease will be measured using a clinical event scale of disease severity evaluated up to Day 28:
  1. Death
  2. Requiring mechanical ventilation and/or in ICU
  3. non-ICU hospitalization, requiring supplemental oxygen;
  4. non-ICU hospitalization, not requiring supplemental oxygen, or a stay of >24 hours for observation in an ED, field hospital, or other healthcare unit\*, or any receipt of O2 for >24 hours, outside of hospital\*
  5. Not hospitalized, but with clinical and laboratory evidence of COVID-19 infection (symptomatic infection)
  6. Not hospitalized, no clinical symptoms compatible with COVID-19, but with laboratory evidence of COVID-19 infection (asymptomatic infection)
  7. No symptoms compatible with infection, no laboratory evidence of COVID-19 (No indication of infection)

*Other Outcomes:*

- Comparison of anti-SARS-CoV-2 titers at days -1 to 0, 1, 7, 14, and 90 days after transfusion between those randomized to HCIP and control plasma
- Comparison of rates and durations of SARS-CoV-2 PCR positivity (RT PCR) at days -1 to 0, 1, 7, 14, and 28 between treatment groups
- Comparison of levels of SARS-CoV-2 RNA amongst those randomized to HCIP vs. control plasma at days -1 to 0, 1, 7, 14, and 28

## **Power and Sample Size**

We hypothesize that outpatient adults with recent exposure to COVID-19 who receive HCIP will have a lower incidence of developing a SARS-CoV-2 infection with COVID-19 when compared with similar adults receiving control plasma. A sample size of 500 individuals with a high risk exposure within 96 hours of enrollment with a 1:1 allocation ratio to each treatment group will have 80% power to detect a 50% reduction in cumulative incidence by 28 days. This is with a one-sided type 1 error of 5% as we are solely interested in superiority. We assumed that the probability of incident COVID-19 cases is between 0.10 and 0.20 in the control population. We explored several different scenarios with an exponential model to identify the lambda parameter and the package 'powerSurvEpi' for the R statistical software was then used to calculate the sample sizes for these scenarios (See Table1). We assumed that the cumulative incidence of symptomatic disease in SARS-CoV-2 exposed individuals randomized to control plasma to be 0.13X by day 28 and 0.065 (50% reduction in risk) by day 28 among those randomized to HCIP. We therefore estimated 488 participants (244 in each arm). It is

---

\*with surge of infections in December 2020 and hospitals becoming more full, these two were put into the clinical events scale as hospitalization equivalents

anticipated that very few of these subjects will be randomized and not start study plasma infusion (and so be excluded from the primary analysis). Furthermore, it is anticipated that there will be low loss to follow-up prior to development of disease or 28 days (and so have missing data for the primary endpoint). Therefore, we have extended the total sample size to 500 participants. For all analyses, we will use a modified intention-to-treat analyses, which excludes randomized subjects who do not initiate an infusion of the study plasma.

Table 1: Total sample size by the incident proportion of COVID-19 among controls and by percent risk reduction

Proportion of Incident COVID-19 cases at day 28 among controls	50% Risk Reduction	75% Risk Reduction
0.10	648	199
0.13	488	150
0.15	415	129
0.20	298	94

## Randomization

The Data Coordinating Center (DCC) will work with the EDC developers (Prelude Dynamics) to generate random treatment assignments using a documented process. The randomization schedule will be designed to yield an expected allocation ratio of 1:1 for HCP + control plasma. Assignments will be stratified by clinical site and schedules will employ permuted block designs, with block sizes to be determined and documented at the DCC. Adjustment for residual or other imbalances in the baseline composition of the treatment groups, if needed, will be done using multiple regression techniques rather than through further stratification in the design.

Treatment assignments will be masked to the participants and the personnel of the clinical sites, but not to an unmasked statistician associated with the DCC. This unmasked statistician will only provide unmasking information (1) to the DSMB, (2) if required for participant safety, and (3) to the analytical team after databases have been locked. Unforeseen circumstances that may require unmasking will need to be approved by the Steering Committee. Staff in the blood banks will also be unmasked to treatment assignments

Treatments will be assigned at the baseline visit using an online program accessible to the clinical sites. After the entry of specified pre-randomization data, each enrolled participant's ID will be irrevocably linked to the next unassigned treatment for that clinical site. Upon notification of a randomization, an unmasked email is sent to the blood bank informing of the participant identifier and the treatment group assignment. Blood bank personnel will select an appropriate unit of plasma for transfusion and will mask (over-label) the unit consistent with local and federal regulations. The data system will also check for and prevent duplicate assignments (same participant randomized more than once). The treatment assignment tables in the data system will be encrypted to prevent inadvertent disclosures.

The procedures related to randomization of participants at the clinical sites will be as follows:

- Clinical sites will collect randomization eligibility and baseline data on the appropriate data collection instruments and will enter these data into the database.
- The data system will confirm randomization eligibility, issue the next assignment, and will relay treatment assignments to the DCC (masked) and blood bank (unmasked) as described above.
- The data system will automatically store the date and time of assignment, the identity of the clinical site personnel making the assignment, the participant's ID, and the treatment group assignment.

The data system will provide access to randomization materials, including a visit schedule and allowable time windows for visits.

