Our analysis will be a time to event analysis examining the effect of anti-SARS-CoV-2 plasma. We will estimate the survival function for each treatment arm in order to estimate the risk difference over time as well as the restricted mean survival time which is the area under the survival function and provides the expected mean time to hospitalization or death up to time t^{22} . Our approach will be to estimate the cumulative incidence using the doubly robust estimator based upon targeted minimum loss based estimator as described by Diaz et al [Díaz, I., Colantuoni, E., Hanley, D.F. *et al.* Improved precision in the analysis of randomized trials with survival outcomes, without assuming proportional hazards. *Lifetime Data Anal* **25**, 439–468 (2019)]. By adjusting for baseline covariates that are related to the outcome, we increase precision. The TMLE based approach was shown to increase precision by around 10% to 20% over an inverse probability weighted or augmented inverse probability weighted estimator. As stated above, we will use a hybrid approach of adjusting for pre-specified variables (age) and an algorithmic approach to identify additional variables related to the outcome. Specifically, a random survival forest will be used to identify variables that are related to the outcome in order to increase precision. We will use a random survival forest blinded to the treatment arm allocation and *not* including an indicator variable for treatment. The following pre-randomization variables will be considered: clinical site, race, ethnicity, sex, category of exposure, hematology factors and other laboratory markers (i.e., CBC and metabolic panels), body mass index, ABO blood group, targeted physical exam, and prior comorbidities that have specifically been associated with worse COVID-19 outcomes including: asthma, chronic kidney disease, chronic lung disease (COPD, idiopathic pulmonary fibrosis, cystic fibrosis), diabetes, hemoglobin disorders (thalassemia, sickle cell disease), immunocompromised (cancer, HIV, organ transplantation, prolonged use of corticosteroids), chronic liver disease,

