Analyses will be done to explore differences in the outcomes between the treatment groups. Results of these analyses will be presented unadjusted (crude) and adjusted for covariates. Variables chosen for adjustment are specifically for increasing precision in estimates of treatment efficacy and thus must be predictive of disease outcome [Diaz et al, Lifetime Data Anal (2019): 25]. To identify the adjustment variables, we will utilize a hybrid approach of pre-specifying some variables and using an algorithmic approach to identify variables to adjust for among pre-specified candidate variables. Variables that we are near certain to be predictive of outcome will be adjusted for. Age has been consistently related to worse outcomes for COVID-19 and therefore will be included in analyses for adjustment. Other pre-specified variables that will be candidates for inclusion in primary analysis will be determined via an algorithmic approach and these variables will include: clinical site, race, ethnicity, sex, category of exposure, hematology factors and other laboratory markers (i.e., CBC and metabolic panels), body mass index, ABO blood group, prescription steroid, targeted physical exam, and prior comorbidities that have specifically been associated with worse COVID-19 outcomes including: asthma, chronic kidney disease, chronic lung disease (COPD, idiopathic pulmonary fibrosis, cystic fibrosis), diabetes, hemoglobin disorders (thalassemia, sickle cell disease), immunocompromising conditions (cancer, HIV, organ transplantation, prolonged use of corticosteroids), chronic liver disease, hypertension, and serious heart conditions (heart failure, coronary artery disease, cardiomyopathies, pulmonary hypertension), obesity, smoking status, dementia, down syndrome, pregnancy, stroke/cerebrovascular disease, and substance use disorders [updated to CDC list on website on 5/29/2021 and Guan et al Eur Respir J. 2020 May; 55(5)]. To determine which of these pre-specified candidate variables to be included, we will conduct variable selection by random survival forest in the entire sample (i.e., not including an indicator term for treatment arm) and blinded to treatment allocation. The variable importance and 95% confidence intervals [Ishwaran et al Statistics in Medicine. 2019;38] shall be used to identify predictive variables for the outcome and included in analytical models. Specifically, variables in which the 95% CI for the variable importance from the random forest does not contain 0 will be adjusted for. This should reduce the number of variables that the analysis adjusts for in order to minimize the degrees of freedom that are used while allowing the analysis to include the variables that have the most correlation with the outcome in order to maximize precision. This hybrid approach will be done on the full sample (i.e., modified ITT sample) and not include the treatment arm (i.e., among entire sample without controlling for convalescent or control plasma) in order to identify the prognostic baseline variables for entire sample.

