
The pre-randomization variables listed above (age and the pre-specified candidate variables) will be explored and described according to summary statistics (mean and variance or 25th, 50th, and 75th

percentiles or proportion as appropriate for type of variable) by treatment group and overall. Analyses will be done in the R statistical software.

There will be two formal reviews of interim results. The first will be after 15 infections which is expected to occur near 150 participants reaching day 28 and the second after 50% of the total recruitment has been achieved and these individuals followed to at least day 28. Interim analyses will only be adjusted for age. Stopping guidelines will be based on O'Brien-Flemming boundary. The interim analysis Z-value boundary of 3.03 (nominal p-value of 0.0011, spent alpha 0.0011), 2.38 (0.0087, 0.008), and 1.68 (0.464, 0.408) for a one-sided test with Type 1 of 0.05.

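### Randomisation is stratified by clinical site, but site is only a candidate covariate at the final analysis and is left out of both interims, so the tests can be slightly conservative.

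*SAP*

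**What the plan says.** **Design.** The SAP (Randomization) states: "Assignments will be stratified by clinical site and schedules will employ permuted block designs". Site is the only stratification factor named. Block sizes are left to the data coordinating center. Protocol 4.3.5 gives the 1:1 ratio but does not mention stratification.

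**Final analysis.** Age is the one covariate certain to enter: "Age has been consistently related to worse outcomes for COVID-19 and therefore will be included in analyses for adjustment" (SAP, Statistical Principles). Site heads the list of candidates: "clinical site, race, ethnicity, sex, category of exposure, hematology factors and other laboratory markers". A candidate enters by this rule: "variables in which the 95% CI for the variable importance from the random forest does not contain 0 will be adjusted for". Protocol 5.2 gives site the same status: "The following pre-randomization variables will be considered: clinical site, race, ethnicity, sex, category of exposure".

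**Interim analyses.** "Interim analyses will only be adjusted for age" (SAP, Statistical Principles). Protocol 8.3 and the SAP's Interim monitoring section agree.

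**Imbalance.** The Randomization section adds that adjustment for residual imbalance, "if needed, will be done using multiple regression techniques rather than through further stratification in the design". That is conditional and does not make site mandatory. Neither document specifies a site-stratified test or a variance estimator that allows for the stratified allocation.

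**The concern.** Permuted blocks within site keep the arms close to balanced at every site, which removes most between-site variation in risk from the treatment comparison. An analysis that ignores site still counts that variation in its standard error. If infection risk differs between sites, the reported standard error is then larger than the true one, the test rejects too rarely under the null, and some power is given away.

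The SAP justifies its covariate strategy by precision. It nevertheless leaves its only design factor to a screen at the final analysis and omits it at both interims. The screen may have little to work with: at the planned rates the mean event probability is (0.13 + 0.065)/2 = 0.0975, so 500 participants yield about 49 events, or roughly 2 to 5 per site over an assumed 25 or 10 sites.

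**Working it through.** **1. Reproduce the planned sample size** (SAP, Power and Sample Size: 0.13 vs 0.065 by day 28, one-sided 5%, 80% power, 1:1, N = 488).
- Exponential hazard ratio = ln(1 − 0.065)/ln(1 − 0.13) = 0.4826.
- Schoenfeld events = 4(1.645 + 0.842)²/(ln 0.4826)² = 46.6, rounded up to 47.
- N = 46.6/0.0975 = 478, or 47/0.0975 = 482. The stated 488 is within 3%. The calculation has no term for site.

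**2. Mechanism.** A site-blind test uses the variance p(1 − p). With balanced sites the variance that applies is p(1 − p) − Var(p_s), where p_s is the risk at site s. To first order Var(p_s) ≈ [p(1 − p) × SD]², with SD on the logit scale. At p = 0.13 in both arms, p(1 − p) = 0.1131.
- SD 0.5: Var ≈ (0.1131 × 0.5)² = 0.0032; SE ratio = √(0.1131/0.1099) = 1.014.
- SD 1.0: Var ≈ 0.1131² = 0.0128; SE ratio = √(0.1131/0.1003) = 1.062.

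These are rough ceilings: incomplete blocks and a finite number of sites reduce them.

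**3. Simulation.** Inputs from the documents: risks 13% and 6.5% (equal risks for type I error), 1:1 allocation, Z boundaries 2.38 and 1.68, N = 250 at the second interim and 500 at the end. Assumptions: 10 or 25 sites of unequal size, blocks of 4, normal site effects on the logit scale, 20,000 trials per scenario. An unadjusted risk-difference test is compared with a site-stratified Mantel-Haenszel test. Each cell gives 10 sites / 25 sites. Arrows run from site ignored to site-stratified.

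| Site SD (logit) | Model SE ÷ true SE, site ignored (null) | Type I error at Z 1.68, site ignored | Final power, % | Crossing at second interim, % |
|---|---|---|---|---|
| 0 | 1.000 / 1.005 | 0.0461 / 0.0459 | 79.04→78.83 / 79.03→78.66 | 25.01→24.69 / 24.94→24.32 |
| 0.5 | 1.000 / 1.014 | 0.0461 / 0.0447 | 77.96→78.12 / 78.95→79.15 | 25.21→25.72 / 25.09→25.04 |
| 1.0 | 1.026 / 1.047 | 0.0413 / 0.0381 | 76.26→77.32 / 78.24→79.29 | 25.34→28.03 / 24.80→27.38 |
| 1.5 (extreme) | 1.065 / 1.102 | 0.0345 / 0.0326 | 73.58→75.91 / 77.26→79.96 | 25.89→30.91 / 24.70→30.05 |

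The nominal one-sided level at Z 1.68 is 0.0465. The stratified test held 0.045 to 0.048 throughout. Monte Carlo error on one power figure is about √(0.79 × 0.21/20,000) = 0.3 points, but both tests are run on the same trials.

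Differences from the table:
- Final power lost by ignoring site: 0.16 to 0.20 points at SD 0.5; 1.05 to 1.06 at SD 1.0; 2.3 to 2.7 at SD 1.5.
- Second-interim crossing lost: −0.05 to 0.5 points at SD 0.5; 2.6 to 2.7 at SD 1.0; 5.0 to 5.4 at SD 1.5.
- Cost of stratifying when site has no effect: 0.2 to 0.4 points of final power; 0.3 to 0.6 points at the second interim.

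**4. First interim** (15 infections, about 150 participants, Z 3.03). The chance of crossing is about 3 to 3.5% with site ignored and 3 to 4.4% with stratification for SDs up to 1.0. Fifteen events over 10 or 25 sites is 1.5 or 0.6 per site. On a Poisson count, e^(−1.5) = 22% to e^(−0.6) = 55% of sites would have no event, so a separate term per site is not workable.

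**The case against.** The strongest reply is that the simulation compares never adjusting for site with always adjusting, while the final analysis does neither. The forest screens for prognostic variables, and omission costs something only when site is prognostic. The scenarios with the larger losses are those where selection is more plausible. Other candidates, such as category of exposure, could also absorb some of the site variation. This stands: the final-analysis figures are upper bounds. It does not apply at the interims, where the forest is not used and site is always omitted.

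A second reply is that adjustment is not arbitrary. The selection rule is pre-specified, run on the pooled sample and blind to treatment. This also stands. A reader might infer that data-driven selection of site, or its omission, biases the estimate or inflates type I error. The documents do not support that: selection does not use treatment, and the simulated error lies at or below nominal.

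A third reply concerns the premise. Nothing in the documents shows that risk differs strongly between sites. All participants enter after a close contact within 96 hours and a negative molecular test, which may narrow differences. A reader might therefore infer a material loss of power that the plan cannot be shown to have.

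Finally, a reader might take site adjustment as free. It is not: per-site terms fail at the first interim, and stratifying costs a little if site is not prognostic.

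**Conclusion.** The point holds as a modest precision issue. The plan does not guarantee that its only stratification factor is accounted for at the final analysis, and it certainly omits it at both interims. The consequence is conservatism only.

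For an assumed between-site logit SD of 0.5 to 1.0, the standard error is about 0-5% too wide and one-sided type I error is 0.038 to 0.046 against a nominal 0.0465. Final power falls by at most about 0.2 to 1 point, and the chance of crossing at the second interim by about 0 to 2.7 points. If site is not prognostic, nothing is lost.

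The number and size of sites, the block size and the between-site SD are all assumed. The simulation uses binary day-28 tests without age, not the planned targeted minimum loss-based estimator, so the sizes are indicative. Confidence is high on what the documents say and on the direction, and limited on the size.

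**What to change.** - **Final analysis.** Remove clinical site from the random-forest candidate list in the SAP and in Protocol 5.2. State that the primary analysis and the symptomatic-infection analysis will account for site as well as age. Pool sites below a fixed size by a rule written before unblinding.
- **Interim analyses.** Replace the age-only rule in the SAP and in Protocol 8.3 with one that also accounts for site, through a site-stratified test or a variance estimator that reflects the stratified allocation. Do not fit a separate term per site with about 15 events. The same approach is an acceptable alternative at the final analysis.
- **Consistency.** Add the stratification by site to Protocol 4.3.5.

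The cost is wording and a pooling rule, with no new data or participants. If site proves not to be prognostic, expect to give up about 0.2 to 0.4 points of final power.

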### **Primary Analysis:**

Our primary hypothesis is that by providing anti-SARS-CoV-2 plasma, the cumulative incidence of the development of active infection will be lower among the individuals receiving HCIP as compared to those receiving control plasma over the course of follow-up. Therefore, our primary endpoint is the development of COVID-19 within the follow-up period. For clarity the working definition of our endpoint is positive for SARS-CoV-2 by molecular test with or without any symptoms compatible with COVID-19. To allow to differentiate between all infections and asymptomatic infections, the analyses will be done using 1) all infections as indicated by research based RT-PCR or capture of positivity by clinical testing and then again for 2) symptomatic infection based upon symptoms compatible with COVID-19 infection and being positive by molecular test (research sample or clinical result). For the primary analysis, individuals who test positive by a molecular test on the calendar day of transfusion will be excluded from the analysis. Individuals whose specimens obtained at screening visit who test positive on two antibody tests done by [name] laboratory using the Euroimmune assay and [name] using antibody ELISA end point titer and area under curve, will be excluded as indication of a prior unknown COVID-19 infection.

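### The SAP's open-ended adjustment for baseline imbalance is not reconciled with its blinded covariate selection, and the selection rule has two wording errors

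*SAP*

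**What the plan says.** The SAP speaks about covariate adjustment in two places.

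- **Randomization.** After describing site-stratified permuted blocks, the SAP says: "Adjustment for residual or other imbalances in the baseline composition of the treatment groups, if needed, will be done using multiple regression techniques", and continues "rather than through further stratification in the design". The same section releases treatment codes "to the analytical team after databases have been locked".
- **Statistical Principles and Primary Analysis.** Here the purpose of adjustment is precision: "Variables chosen for adjustment are specifically for increasing precision in estimates of treatment efficacy and thus must be predictive of disease outcome". Age is always included. For the remaining named candidates, "we will conduct variable selection by random survival forest in the entire sample", without the treatment indicator and blinded to allocation. The inclusion rule is that "variables in which the 95% CI for the variable importance from the random forest does not contain 0 will be adjusted for". The data set is also named: "This hybrid approach will be done on the full sample (i.e., modified ITT sample"). The primary test is the covariate-adjusted TMLE comparison at day 28.

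The modified ITT set is defined in Power and Sample Size and again in Statistical Principles; its only exclusion is of randomized people who never start the infusion. Primary Analysis then removes two further groups. One is defined by "individuals who test positive by a molecular test on the calendar day of transfusion will be excluded from the analysis"; the other is people whose screening specimen is positive on two antibody tests.

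Protocol section 5.2 describes the same TMLE and blinded forest. Protocol section 4.3.5 (Randomization) has no sentence on imbalance.

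**The concern.** Choosing covariates without sight of the arms protects the primary test from a model picked for its result. A second, conditional adjustment rule that depends on comparing the arms does not have that protection. Imbalance cannot be seen until the arms are known, and the analytical team learns them only after database lock, when outcomes are also in hand. The trigger is undefined, the covariates are not listed, and the method (multiple regression) is not the primary estimator. If the rule were applied to the primary comparison, there would be two adjusted results and no statement of which governs.

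The selection rule has two separate faults.

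- An interval that excludes zero can lie wholly below it. Negative importance means that the variable worsens prediction, which is the opposite of the stated aim.
- Variables are selected in a population that includes people whom the primary analysis removes: those molecular-positive on the day of transfusion and those already seropositive. What predicts the recorded outcome in them may differ from what predicts infection in susceptible participants.

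**Working it through.** **1. The two adjustment rules side by side**

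| Feature | SAP, Randomization | SAP, Statistical Principles and Primary Analysis |
|---|---|---|
| Reason to adjust | Imbalance between arms | Precision; variable must be prognostic |
| Needs arm labels | Yes | No |
| Trigger | Conditional, undefined | Always applied, by a mechanical rule |
| Covariates | Not listed | Age plus a named candidate list |
| Method | Multiple regression | TMLE |
| Analysis it applies to | Not stated | Primary analysis named |

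The sensitivity analyses listed under Primary Analysis include no imbalance-adjusted analysis, so the Randomization sentence has no stated home. Statistical Principles has the baseline variables summarised by treatment group, so any imbalance will be visible.

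**2. How likely is the condition to arise?**

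Assume 30 independent baseline covariates (an assumption; the true candidates are correlated). The chance that at least one differs between arms is 1 − 0.95^30 = 0.785 at p<0.05, and 1 − 0.90^30 = 0.958 at p<0.10.

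**3. Size, if the better of two results were taken as final**

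The plan's final boundary is Z = 1.68. P(Z > 1.68) = 0.0465, which agrees with its one-sided threshold of p = 0.047.

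For two Z values with correlation ρ under the null:

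P(at least one > 1.68) = 2 × 0.0465 − P(both > 1.68)

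| ρ (assumed) | P(both > 1.68) | P(at least one > 1.68) | Excess over 0.0465 |
|---|---|---|---|
| 0.99 | 0.0410 | 0.0520 | 0.0055 |
| 0.95 | 0.0343 | 0.0587 | 0.0122 |
| 0.90 | 0.0294 | 0.0636 | 0.0171 |

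**4. Cross-check by simulation under the null**

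Settings (assumptions, except the 500 participants and the 13% risk): 500 participants, 13% risk in both arms, 30 independent covariates of which 1 to 6 are prognostic, a linear risk-difference model with robust standard errors, one-sided cut-off 0.0465, and 4,000 runs per setting (Monte Carlo standard error about 0.35 points). Imbalance was flagged at p<0.05 or p<0.10.

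| Strategy | Rejection rate |
|---|---|
| Fixed model | 4.1–5.3% |
| All imbalanced covariates added by a fixed rule | 3.8–5.3% |
| Most favourable of the fixed and imbalance-adjusted models | 5.1–6.3% |

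In the same runs, the third strategy exceeded the fixed model by about 0.6 to 1.5 points. The fixed imbalance rule gave no inflation. The risk therefore comes from discretion over which result to report, not from adjusting for imbalance as such.

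**5. The selection rule**

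No arithmetic applies. For an importance interval (L, U), the text admits a variable if L > 0 or if U < 0. The stated aim, variables predictive of outcome, corresponds to L > 0 only. For the data set, modified ITT requires only that transfusion was started; the primary set is modified ITT minus the molecular-positive and seropositive exclusions. The first contains the second, and the two differ whenever anyone meets either exclusion. The documents do not give the number of such people.

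**The case against.** A reader might infer that the Randomization sentence reopens the primary model after unmasking and so voids the protection of blind selection. The documents do not support that reading.

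- The sentence does not mention the primary analysis or any step after unmasking.
- Its closing words set regression against further stratification, so it reads mainly as the reason for stratifying by site alone.
- The specific analysis text is closed: a named candidate list, a mechanical blinded rule, and no imbalance criterion.
- The primary estimator is TMLE, so naming multiple regression suggests that the sentence was not written as a rule for the primary model.
- Statistical Principles requires crude and adjusted results to be presented, so an altered model would not stand alone.
- No text lets analysts choose between final results, and the error rates above need such a choice.

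All of this stands, and it limits the point to an ambiguity. It does not remove the ambiguity. The sentence is still a commitment to adjust on observed imbalance, it is assigned to no analysis, and nothing says that the blinded procedure satisfies it.

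On the selection rule, the intent is clear from the surrounding text, a useless baseline covariate does not bias a randomized comparison, and reference to the full sample is partly there to contrast pooled with arm-specific selection. That is fair. It makes these matters of precision and exact wording, with no demonstrated effect on the result.

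**Conclusion.** The concern holds as an unreconciled ambiguity, not as a stated change to the primary model. The SAP leaves open whether an adjustment that depends on seeing the arms could enter the primary comparison.

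The cost is modest and conditional. If the more favourable of two results were reported, the one-sided error would be about 0.5 to 1.7 points above 0.0465. This rests on assumed correlations of 0.99 to 0.90 and on a choice that the plan does not grant. The simulation gives a similar excess under its own assumptions, and none when the imbalance rule is fixed.

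The selection rule is wrong as written in two ways: it admits wholly negative importance, and it uses the modified ITT set rather than the primary analysis set. Both can cost precision. Because selection stays blind to arm, neither favours a treatment group. The documents do not allow the loss of precision to be estimated.

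**What to change.** Three edits to the SAP, made before the arms are released:

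1. **Randomization.** Keep the reason for not stratifying further, and add that the blinded procedure in Statistical Principles is the only covariate adjustment in the primary analysis. State that any imbalance-driven adjustment is a labelled sensitivity analysis, with its trigger and covariates fixed before database lock.
2. **Statistical Principles, inclusion rule.** Require the lower limit of the 95% interval for variable importance to be above zero.
3. **Statistical Principles, data set.** Run the selection, still blinded to arm, on the participants who remain after the molecular-positive and seropositive exclusions in Primary Analysis.

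The cost is a few lines of wording. Sample size, power, alpha and trial conduct do not change.
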